[name] Research Bio. Med. Lab. Technologist SDCN Aalborg University

[name] [name]. SDCN Aalborg University Hospital

II. BACKGROUND AND SIGNIFICANCE

A. Background

Diabetes Mellitus (DM) is a growing healthcare problem worldwide[1] and currently affects more than 451 million people[2]. DM is associated with excess morbidity and mortality[3][4] with diabetic peripheral neuropathy (DPN) being the most common of the classic diabetic complications[5]. This means, that half the diabetic population will develop DPN during their lifetime[6]. Moreover, DPN is also the leading cause for disability in diabetic patients, mainly due to its complications including autonomic disturbances and events related to the diabetic foot. The most important being diabetic foot ulcers, foot amputations, and the Charcot neuroarthropathy (CN), while approximately 20-30% of patients will suffer from invalidating neuropathic pain at some point during their lifetime[7]. Furthermore, diabetic foot ulcers have been associated with ischemic heart disease (IHD), which is the leading cause of premature mortality in patients with DM[8]. At the same time, the five-year mortality after new-onset diabetic ulceration have been reported to be 43-55%, and 74 % in patients with diabetic foot amputation, which is significantly higher than the five-year mortalities for many forms of cancer[9].

Despite this, our knowledge is quite limited when it comes to risk stratification of the diabetic patients. It is clear that DPN is the single most important risk factor for development of complications regarding the diabetic foot whether talking about foot ulcers[10], amputations[11], or CN[12]. However, the current clinical tests to detect DPN are unspecific and with questionable sensitivity reported as low as 0.53[13]. Furthermore, the current clinical tests are solely assessing large fiber neuropathy and are not able to do a meaningful grading of the severity of the neuropathy, hence the need for new methods to provide efficient clinical outcome measures and useful clinical endpoints.

B. State-of-the-Art

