Diabetic peripheral neuropathy (DPN) is the most common complication to advanced diabetes mellitus (DM)[14], and is strongly associated with invalidating and life-threatening complications like foot ulcers[15][16], CN [17][18], painful neuropathy[19], risk of fall and fracture[20], and lower foot amputations[11]. The incidence of DPN is reported with great variance, but several large studies have reported numbers around 20% for DM type I[21][22][23] and 50 % for DM type II[24]. Furthermore, patients with foot pathology attributable to DPN exhibit significantly higher mortality rates than those solely attributable to vascular diseases. This applies to both non-infectious neuropathic foot ulcers[25] and acute CN [26].

At this point no treatment for the underlying nerve damage of DPN is available[27], and the pathogenesis is still not fully understood[28][29][30]. Therefore, current strategies focus on prevention of the initial nerve damage using annual screening-tests targeting large nerve fibers. Available tests for large-fiber function include vibration perception, proprioception, 10-g monofilament, and ankle reflexes[31]. Tests for small-fiber function are not routinely used, but include pinprick and temperature sensation[31]. Most studies have reported that early stages of DPN mainly affect the small nerve fibers[32][33] raising the question of why these are not used in standard screening. However, mixed results do exist, as some studies have reported simultaneous development of DPN in small- and large nerve fibers[34][35]. The most common clinical tests (monofilament) have recently been reviewed, showing low sensitivity when trying to detect early neuropathy[13][36], but wielding fine results when detecting severe neuropathy[37].

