
III. STUDY OBJECTIVES

To test Perception Threshold Tracking (PTT) and multi-level MRI as methods for early detection and grading of severity of neuropathy in patients with diabetes mellitus.

To use multi-level MRI for characterization of peripheral and central nervous system changes related to neuropathy in patients with diabetes mellitus.

To compare Perception Threshold Tracking (PTT) and MRI to methods of traditional clinical practice and established methods of clinical research like Corneal Confocal Microscopy (CCM) and Quantitative Sensory Testing (QST) as well as axon flair-mediated neurogenic vasodilation (AF).

To test reliability of different measurements of neuropathy.

A better understanding of the underlying neuropathy of diabetes and new methods for early, reliable detection of DPN could result in intensified treatment and prophylactic measures prolonging of the complicationfree period of diabetes mellitus. Ultimately, this could potentially result in fewer complications related to the diabetic foot, and maybe even prolonged overall-survival and reduced healthcare cost.

IV. METHODS

A. Study Design

This study is a prospective, observational, cross-sector study starting March 1, 2019 running until December 1, 2021. The study will be conducted on patients from Aalborg University Hospital. Participants will be informed about the trial both written and vocally and no changed in antidiabetic medication will be performed. The instruments will include Corneal Confocal Microscopy (CCM), Quantitative Sensory Testing (QST), axon flair-mediated neurogenic vasodilation (AF), handheld heart rate measurement device (Vagus[™]), cuff, and MRI, which are all established methods of clinical research. Furthermore, participants will be tested using monofilament and Biothesiometry, which equals actual clinical practice, and with Perception Threshold Tracking (PTT), which is a new take on an older, well-known technology. Further tests will include a handheld pinprick device, measurements of peripheral arterial disease (PAD) and conventional NCS. The main endpoint of the study will be sensitivity/specificity of all examinations, as well as a comparison of the newer methods against more well-established modalities.

B. Study Population

The study population include four well-defined groups of subjects:

- 1. Patients with Type 1 diabetes and painful diabetic peripheral neuropathy (DPN).

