- 2. Patients with Type 1 diabetes and non-painful diabetic peripheral neuropathy (DPN)
- 3. Patients with Type 1 diabetes and without diabetic peripheral neuropathy (DPN).
- 4. Healthy control subjects matched for age, BMI, and gender.

Diabetes duration, HbA1c, insulin use, ethnicity, and co-morbidities will be matched between group 1, 2 and 3 to best ability.

Inclusion criteria:

- 1. Men and women minimum 18 years of age and maximum 70 years of age
- 2. Signed informed consent form
- 3. Diagnosed with diabetes type I (for group 1-3)
- 4. Diagnosed with DPN defined as a threshold above 25-volt biothesiometry or absent feeling on the big toe using 10g-monofilament. (for group 1-2)
- 5. Answered questionnaire: PainDETECT
- 6. Nothing abnormal on initial tests (group 4)
- 7. Accepted initial screening blood samples
- 8. MRI-compatible participant

Exclusion criteria:

1. Current or previous alcohol- or drug abuse

- 2. Abnormal screening blood samples
- 3. Not being able to understand Danish written and/or verbally
- 4. Not being able to corporate to examination (e.g. not being able to speak, suffering from senile dementia etc.)
- 5. Previous chemotherapy or intake of experimental medicine
- 6. Active HSV- or VZV-infection or known HIV
- 7. Known severe skin disease
- 8. Known neural damage or disease in the neural system (e.g. MS, Guillain-Barre etc.)
- 9. Critical limb ischemia defined as in current clinical consensus[63]
- 10. Allergy or intolerance to histamine or inability to make do without for one day
- 11. Pregnancy
- 12. Active cancer-disease

C. Assessment of Resources

The study will be conducted in collaboration with Steno Diabetes Center Northern Denmark (SDCN) and Department of Radiology, Aalborg University Hospital. SDCN has access to patients with diabetes and can provide the necessary premises.

The study will be conducted in collaboration with Center for Neuroplasticity and Pain (CNAP), Aalborg University and SDCN, who have the technical and financial resources needed to establish the setup and conduct the examinations. Furthermore, an experienced research Bio. Med. Lab. Technologist is signed for the project thereby, alongside the Ph.D.-students, ensuring trained personnel. The study is set for a long inclusion, but additional time is available if required, as the Ph.D.-students are employed until 31st of October 2022.

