The blood samples will be taken and handled as usual by the biochemical department and will be destroyed after usage. No biobank will be made. All samples will start being analyzed immediately (within 2h), however, some samples (like vitamin D) will take some time to analyze. All results will be available within 10-12 days but samples will always be destroyed as soon as the analysis has been initialized.

V. DATA COLLECTION

Patient data will be collected using the electronic patient journal (EPJ) after consent of the participant. Only patients with an active continuity of care at SDCN will be included (as well as healthy controls). The principle investigator is employed at SDCN as a medical doctor alongside one of the Ph.D.-students.

Data collected will include demographic data such as name, age, sex, weight, and height, and clinical information related to diabetes, such as type, duration, medication, complicating peripheral arterial disease, and status of complications. This to ensure correct grouping of the patients and to make sure that they meet the inclusion criteria.

VI. DATA ANALYSIS

A. Sample Size Considerations

The following sample size estimation is made on the ability to separate a group of diabetic patients without neuropathy from a group of diabetes patients with 'moderate' neuropathy. The calculations are based on published measurement of the sensory nerve action potential amplitude in nerve fiber conduction assessments[45]. Setting the significance level to 0.05 and the power to 0.8 results in a sample size estimation of 16 persons in each group. $n = \frac{15.7*\sigma^2}{d^2} = \frac{15.7*(4.7^2+7.5^2)}{(14.4-5.7)^2} = 16$. The study involves several experiment measures, but we expect that max 20% of the measures will be dropouts. The number of participants needed to be recruited in each group will therefore be $N = \frac{n}{1-dropout} = \frac{16}{0.8} = 20$. We want to compare four groups as defined in section IV.B. Study Population. The total number of participants will therefore be 80.

B. Statistical Methodology

The data will initially be analyzed by a series ANOVA test to compare each measurement between the four groups.

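### With group status as reference, the accuracy endpoint cannot support the early-detection objective and can penalise a method that finds early neuropathy

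*Combined protocol and SAP*

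**What the plan says.** Section III puts first the testing of PTT and multi-level MRI as "methods for early detection and grading of severity of neuropathy in patients with diabetes mellitus". Section IV.A adds: "The main endpoint of the study will be sensitivity/specificity of all examinations", together with a comparison of newer and established methods. It names no reference standard. Section VI.B reports accuracy from logistic models without naming their outcome.

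Inclusion criterion 4 in IV.B gives the only rule for DPN, for groups 1 and 2: "Diagnosed with DPN defined as a threshold above 25-volt biothesiometry or absent feeling on the big toe using 10g-monofilament". Group 3 is described only as without DPN, with no test criterion attached. The requirement "Nothing abnormal on initial tests (group 4") covers the healthy controls alone.

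On the tests behind that rule:
- II.A says "the current clinical tests to detect DPN are unspecific and with questionable sensitivity reported as low as 0.53", and adds that these tests see large fibres only.
- II.B says of the monofilament: "showing low sensitivity when trying to detect early neuropathy[13][36], but wielding fine results when detecting severe neuropathy[37".
- II.B also reports that most studies place early damage mainly in small fibres, while noting that some find both fibre types affected together.
- IV.D identifies biothesiometry and monofilament as the current clinical standard. It gives nerve conduction studies (NCS) reference status for large-fibre function only.

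Section VI.A sizes the study on "the ability to separate a group of diabetic patients without neuropathy from a group of diabetes patients with 'moderate' neuropathy".

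**The concern.** A method for early detection has to find neuropathy before routine tests do. Here the routine tests form the groups. There is no early-neuropathy group, no follow-up that could later confirm early disease, and no small-fibre reference standard.

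If group membership is the yardstick, two things follow. Sensitivity comes only from people whom the routine tests already call positive, so sensitivity for early disease is not estimated at all. In group 3, a patient with early neuropathy missed by the rule counts as disease-free, so a method that recognises that patient is charged with an error, while a method blind to early disease is not. The comparison of newer with established methods could then favour the wrong one for the stated purpose. Matching group 3 to groups 1 and 2 on diabetes duration and HbA1c (IV.B, to best ability) could raise the number of such patients.

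This is separate from the problem of scoring biothesiometry and monofilament against themselves. It would remain if both were dropped as index tests.

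**Working it through.** **1. The plan's own figure.** n = 15.7 × (4.7² + 7.5²) / (14.4 − 5.7)² = 15.7 × 78.34 / 75.69 = 16.25, printed as 16. Then 16 / 0.8 = 20 per group and 4 × 20 = 80. The figure reproduces. Its inputs are sensory nerve action potential amplitudes, an NCS measure, so the planned contrast is none versus moderate neuropathy on a large-fibre measure. The point here does not depend on this arithmetic.

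**2. Cost of one hidden case.** In group 3 alone: 1/20 = 5 points of specificity (1/16 = 6.25 if 16 remain after dropout). If groups 3 and 4 are pooled as non-DPN: 1/40 = 2.5 points.

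**3. Effect on ranking.** Let q be the share of group 3 with missed early neuropathy and d the fraction of those cases that a method finds. If the method makes no other error, its apparent group 3 specificity is 1 − q × d.

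| q (assumed) | finds all (d = 1) | finds half (d = 0.5) | finds none (d = 0) |
|---|---|---|---|
| 10% | 0.90 | 0.95 | 1.00 |
| 20% | 0.80 | 0.90 | 1.00 |
| 30% | 0.70 | 0.85 | 1.00 |

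The better early detector always shows the lower specificity.

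**4. How large the hidden share might be.** Let p be the frequency of true neuropathy among those classified, and Se and Sp the sensitivity and specificity of the defining rule. The hidden share is h = p(1 − Se) / [p(1 − Se) + (1 − p)Sp]. From the protocol: p = 0.20 (II.B, type 1 diabetes) and Se = 0.53 (II.A). Assumed: Sp = 0.90, p up to 0.50 to allow for matching, and Se up to 0.80 to allow for two tests joined by 'or'.

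| p | Se | h | of 20 | specificity of an error-free method |
|---|---|---|---|---|
| 0.20 | 0.53 | 0.094 / (0.094 + 0.720) = 0.115 | 2.3 | 0.885 |
| 0.50 | 0.53 | 0.235 / (0.235 + 0.450) = 0.343 | 6.9 | 0.657 |
| 0.20 | 0.80 | 0.040 / (0.040 + 0.720) = 0.053 | 1.1 | 0.947 |
| 0.50 | 0.80 | 0.100 / (0.100 + 0.450) = 0.182 | 3.6 | 0.818 |

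At p = 0.20 and Se = 0.53, moving Sp from 1.00 to 0.80 moves h only from 10.5% to 12.8%.

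**5. Sampling error.** A specificity of 18/20 has an exact 95% interval of 68% to 99%. A penalty of two patients is therefore hard to tell from chance, and the data will not reveal it.

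**6. What group 4 can carry.** For a normal limit at mean − 1.96 SD from 20 controls, the standard error is SD × √(1/20 + 1.96²/38) = SD × √(0.0500 + 0.1011) ≈ 0.39 SD. The 95% range of the limit is 1.96 ± 0.76, that is 1.20 to 2.72 SD from the mean. A nominal 2.5% tail could truly be about 12% or about 0.3%.

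**The case against.** Several points on the other side are fair.

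- **The yardstick is not stated.** A reader might infer that early cases in group 3 will be scored as false positives. The documents do not say so. They name neither a reference standard nor a logistic outcome, and with NCS as reference a group 3 patient with abnormal conduction would count as a case. The point must therefore be conditional. NCS would still not cure it for small-fibre disease, given the role that IV.D assigns to it.
- **Group 3 has no explicit criterion.** That it consists of everyone negative on the two tests is an inference. Chart data are collected to support grouping (V), and NCS and a small-fibre pinprick test may be available around inclusion (IV.D). None of these is a stated group 3 criterion. The flowchart figure is missing from the text available for this review.
- **Not every early case need be in group 3.** Low sensitivity is not zero, the rule accepts either test, and II.B reports mixed evidence on which fibres fail first. The explicit statement about early disease concerns the monofilament. For biothesiometry the support is indirect. 'Likely' is as far as the text goes.
- **The inputs are soft.** The 20% is called an incidence and covers all DPN. The 0.53 is a lowest reported value, cited to a review of monofilament tests, and is not the sensitivity of the combined rule. The formula counts any missed neuropathy, not early small-fibre neuropathy specifically.
- **Part of the plan is unaffected.** The four-group ANOVA includes groups 3 and 4, and the correlations and factor analysis do not assume that group 3 is disease-free. But no group 3 versus 4 contrast is named, and none of these yields accuracy for early neuropathy.

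These points limit certainty and size. They leave the mismatch between objective and endpoint in place.

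**Conclusion.** The concern stands in conditional form. If group status is the reference, and the plan offers no other, the main endpoint describes recognition of clinically detectable DPN. It cannot support an early-detection conclusion, and in group 3 it charges a method about 5 points of specificity for each early case correctly found. The comparison of methods can then favour one that is blind to early disease.

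The size is unknown. About 2 of 20 follows from two protocol figures and an assumed specificity of 0.90. The range of 1 to 7 of 20 is illustrative and rests mostly on assumed inputs. A reader might take it as an estimate of bias, or conclude that specificity will certainly be too low for PTT, corneal confocal microscopy (CCM) or thermal testing. The documents support neither. They support a known direction wherever the hidden share is above zero. The limitations in VIII do not mention it.

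**What to change.** Amend VI.B, using data already planned:

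- **(a) Name an early-change analysis.** Prespecify group 3 versus group 4 for PTT, MRI, CCM, Quantitative Sensory Testing (QST) and axon-flare vasodilation (AF), reported as a difference or AUC with a confidence interval. Any share of group 3 outside group 4 limits should be descriptive only. Limits from about 20 controls are imprecise, the controls are selected for having no abnormal result, and many parameters are tested (13 in QST alone). State also that this contrast cannot separate early neuropathy from other effects of diabetes.
- **(b) Limit the accuracy claim.** Name the reference standard and the logistic outcome. State that sensitivity and specificity from groups 1-2 versus group 3 apply to clinically established DPN, and base no early-detection conclusion on them. Align III with this.
- **(c) Add a sensitivity analysis.** Where NCS is available in group 3, show specificity in the NCS-normal part beside the whole group. Note that NCS covers large fibres only and that a positive result with normal NCS is not necessarily false. First confirm coverage, since IV.D justifies NCS as standard for patients with neuropathy.

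The cost is wording and a little analysis, with no new participants or tests. The downside is a narrower claim and imprecise small-group estimates, especially once group 3 is split.

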To avoid 'mass significance' a combined analysis of all measurements will be performed by logistic regression models (LRM) in three steps. This will allow an estimate of the odds ratio and accuracy of each of the measurements and the measurements in combination. First, a series of univariate LRM will be performed for each measurement to investigate the odds ratio and accuracy of the individual. Second, a multiple factor LRM with all measurements as factors will be performed to estimate the odds ratio and accuracy for all measures in combination. Thirdly, factor reduction will be performed to assess the accuracy and odds ratio of a set of independent measures.

Simple bivariate correlation will be performed to further investigate the relation between measurements. Due to the complexity of the measurements a further analysis of the interdependency of the measures using factor analysis will be performed.

VII. DATA AND SAFETY MONITORING PLAN

The project will be reported to the Data protection Agency (DPA), and all sensitive data will be stored in either Red-CAP or on the protected server of Aalborg University Hospital, *"Elektronisk system adgang"* (ESA).

Data are stored in accordance with the stipulations in The Danish Personal Data Protection Act (Persondataloven) and other relevant Danish legislation. If any data processing would occur in foreign countries, the data will be anonymized and handled according to the Danish Data Protection Act.

The data can only be used for the interpretation of this project and will therefore not be of interest to third party.

The project is included in "Region Nordjyllands fællesfortegnelse".

VIII. STUDY LIMITATIONS

Both PTT and QST require corporation from the patients and include subjective measures of pain. As the measured thresholds are not purely objective, psychosocial factors might influence test results.

The study includes diabetic patients exclusively and might not be applicable on populations with different causes of neuropathy.

The expected number of participants are set at 80, thus maybe require additional larger studies to confirm findings.

IX. ETHICAL CONSIDERATIONS

A. Informed Consent

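### The main endpoint reduces mostly continuous readings to sensitivity/specificity, and the newer-versus-established comparison has no sample size and no paired test; a paired ROC-area comparison is a cheap improvement

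*Combined protocol and SAP*

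**What the plan says.** Section IV.A gives the main endpoint: "The main endpoint of the study will be sensitivity/specificity of all examinations, as well as a comparison of the newer methods against more well-established modalities".

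Section VI.A sizes the study on something else, namely "the ability to separate a group of diabetic patients without neuropathy from a group of diabetes patients with 'moderate' neuropathy", using "published measurement of the sensory nerve action potential amplitude in nerve fiber conduction assessments". It reports: "Setting the significance level to 0.05 and the power to 0.8 results in a sample size estimation of 16 persons in each group". Allowing for 20% loss gives 20 per group and 80 in total.

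Section VI.B begins with an ANOVA of each measurement across the four groups. Logistic models follow: "First, a series of univariate LRM will be performed for each measurement to investigate the odds ratio and accuracy of the individual". After these come a model with all measurements, a reduced model, bivariate correlations and a factor analysis. No section gives a target sensitivity or specificity, a confidence-interval width, an ROC area or a paired test between two methods. Nor is there a cut-off for the newer methods. The word accuracy is not defined.

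Section IV.B (inclusion criterion 4) defines DPN by biothesiometry above 25 volts or by failure to feel the 10 g monofilament on the big toe.

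**The concern.** PTT thresholds, most QST parameters, nerve conduction amplitude and biothesiometry are continuous or nearly so. Sensitivity and specificity use only the side of a cut on which a reading falls. The same is true of accuracy in its usual logistic-regression sense, percent correctly classified.

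The ANOVA keeps the full scale, but it compares groups within one measurement. Odds ratios per unit cannot be compared across volts, millinewtons and degrees. Neither tests whether a newer method separates DPN from no DPN better than an established one, which is the second half of the main endpoint. If that question is settled on cut data, a truly better method is more likely to be reported as no different. The 16 per group was not derived for that question.

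**Working it through.** **Inputs from the plan.** Means 14.4 and 5.7, SDs 4.7 and 7.5, multiplier 15.7, 16 per group, 20% loss (VI.A). DPN is groups 1 and 2; diabetes without DPN is group 3 (IV.B). This gives 32 vs 16 after losses, or 40 vs 20 with none.

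**Assumptions (not in the plan).** Newer method's ROC area 0.95 or 0.90; within-group correlation between methods 0.3, 0.5 or 0.7; normal readings; each cut fixed at its true optimum and treated as known.

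**1. The plan's figure.** 15.7 × (4.7² + 7.5²) / 8.7² = 15.7 × 78.34 / 75.69 = 16.25, printed as 16. Then 16/0.8 = 20, and 4 × 20 = 80. The multiplier 2 × (1.96 + 0.84)² ≈ 15.7 already contains the factor 2 that summing the two variances applies again. With the mean variance, 78.34/2 = 39.17, the result is 15.7 × 39.17 / 75.69 = 8.1, or 9 per group. Sixteen per group therefore gives about 97% power for the mean difference, not 80%.

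**2. Implied ROC area of the established measure.** Φ(8.7/√78.34) = Φ(0.983) = 0.837.

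**3. The sizing contrast after a cut.** If the SD of 7.5 belongs to the DPN group, the best cut is 9.32. Sensitivity is Φ((9.32 − 5.7)/7.5) = 0.685 and specificity Φ((14.4 − 9.32)/4.7) = 0.860. With the SDs swapped, the cut is 10.78 and the two values change places. Simulated power at 16 vs 16: t test about 97%, rank test (equivalent to ROC area) about 95%, Fisher 83–85%, uncorrected chi-square 92–93%. Power on this contrast stays above 0.80.

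**4. The between-method comparison.** Established area 0.837; 4,000 simulated studies per row; two-sided 5%. Power (%) is for the DeLong test of the paired ROC-area difference, a z test on the paired difference in sensitivity + specificity, and mid-p McNemar on percent correctly classified.

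| Newer area | n | Corr. | ROC area | Sens+spec | Accuracy | Loss (points) |
|---|---|---|---|---|---|---|
| 0.95 | 32/16 | 0.3 | 42.5 | 37.4 | 36.2 | 5.1, 6.3 |
| 0.95 | 32/16 | 0.5 | 51.9 | 42.1 | 40.9 | 9.8, 11.0 |
| 0.95 | 32/16 | 0.7 | 64.5 | 50.5 | 47.7 | 14.0, 16.8 |
| 0.95 | 40/20 | 0.3 | 53.5 | 43.5 | 43.7 | 10.0, 9.8 |
| 0.95 | 40/20 | 0.5 | 63.2 | 50.2 | 50.0 | 13.0, 13.2 |
| 0.95 | 40/20 | 0.7 | 80.3 | 59.3 | 58.8 | 21.0, 21.5 |
| 0.90 | 32/16 | 0.3 | 13.3 | 12.5 | 11.0 | 0.8, 2.3 |
| 0.90 | 32/16 | 0.5 | 17.0 | 14.5 | 12.2 | 2.5, 4.8 |
| 0.90 | 32/16 | 0.7 | 21.7 | 17.6 | 14.3 | 4.1, 7.4 |
| 0.90 | 40/20 | 0.3 | 16.8 | 14.0 | 13.8 | 2.8, 3.0 |
| 0.90 | 40/20 | 0.5 | 19.8 | 15.8 | 14.8 | 4.0, 5.0 |
| 0.90 | 40/20 | 0.7 | 27.3 | 19.6 | 17.9 | 7.7, 9.4 |

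With equal areas, these tests rejected in 4.2–5.0%, 5.2–6.1% and 4.2–4.7% of runs, so they can fairly be compared. Exact McNemar rejected in only 2.2–2.9%. It would show losses of 15–32 points at area 0.95, but part of that is the conservatism of the test and not the cut. Repeat runs of the same settings gave 5–19 points at 0.95 and 0–11 at 0.90. Only the 40/20, correlation 0.7 row above exceeds 19. Simulation error on a loss is about 1–2 points.

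**5. Cost of choosing the cut in the same data.** Picking the cut that maximises sensitivity + specificity overstates their sum by about 0.08–0.10. The figure runs from 0.06 to 0.12 across areas 0.837 to 0.95, depending on whether the benchmark is the true optimum or the true performance of the chosen cut.

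**6. Precision of the stated endpoint.** The exact 95% CI for a sensitivity of 13/16 is 0.54–0.96; for 26/32 it is 0.64–0.93.

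**The case against.** The strongest reply is that the plan does not rest on cut data. The ANOVA, logistic odds ratios, correlations and factor analysis all use the full scale. Accuracy is undefined and could mean ROC area. Sensitivity/specificity is also how the background section reports other tests, so it is readable and comparable. IV.A states no superiority hypothesis. All of this stands, and it rules out the reading that the plan dichotomises everything. It does not supply a between-method comparison, which the main endpoint promises.

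A reader might infer a fixed penalty, say 9 to 20 points of power. The documents do not support one, because they give no area for PTT or MRI and no correlation between methods. Over a wider set of assumed areas, correlations and group sizes, the loss against accuracy ran from 1 to 27 points. If a cut at 90% specificity were truly known in advance, sensitivity at that cut had more power than ROC area. With that cut estimated from the data, ROC area kept the advantage by about 1 to 32 points. The plan states no such cut for the newer methods.

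A reader might also infer that 16 per group is too few once the sizing measure is cut. Step 3 shows otherwise, because the printed formula counts the variance twice.

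Lastly, ROC area is no cure for the numbers. At 32 vs 16 with area 0.95 it reaches 42–65% power, and at 0.90 only 13–22%. It touches 0.80 in one row of the table, with no losses and correlation 0.7. A much larger gap could reach it: areas 0.90 vs 0.70 at correlation 0.6 gave 87% at 32 vs 16. Nothing in the plan supports assuming such a gap.

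**Conclusion.** The point holds as a cheap improvement, not as a fault that invalidates the study. The main endpoint and the method comparison have no sample-size or precision basis, no paired analysis is named, and accuracy is undefined. For continuous readings, a paired ROC-area comparison usually uses the data better than a comparison of cut readings.

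Under the assumptions listed, the gain is about 5–19 points of power if the newer method's area is 0.95 and about 0–11 if it is 0.90. These ranges depend on the assumed areas and correlations and on an optimal, known cut. They are not a property of the plan.

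One limit applies to any accuracy metric. Biothesiometry and monofilament define DPN, so their ROC area or sensitivity against DPN status is inflated by construction, and comparing PTT with them on that status is biased against PTT.

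**What to change.** **IV.A and VI.B.** For continuous or ordinal measurements that do not define DPN status, make ROC area (DPN versus diabetes without DPN) the main accuracy summary. Compare newer with established methods, for example PTT with CCM, QST or NCS, by the paired difference in ROC area with a 95% CI (DeLong, or a bootstrap over participants). Define accuracy. Report sensitivity/specificity at stated cuts alongside, and as the main result only for tests that are binary by nature. If a cut is chosen in the study data, say so and correct for the optimism.

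**Comparators.** Do not use biothesiometry or monofilament as comparators against the DPN status they define, or label that comparison as biased by construction.

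**VI.A.** State that 16 per group was derived for a mean difference in nerve amplitude. State also that the between-method comparison is not powered at 0.8 by design, whether by sensitivity/specificity, accuracy or ROC area.

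**Cost.** Wording and a little more analysis of data already planned; no extra participants or tests. The downside is that ROC area averages over cut-offs not used in the clinic, so sensitivity/specificity must still be shown.
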